10.3. Attachment 3: ISA-Specific Stopping Rules

The IAC will convene periodically but also when the accumulated safety data triggers one of the stopping rules specified in this ISA. Further enrollment in this ISA, or further dosing in this ISA, or both may be stopped, pending a decision of the IAC.

Stopping rules for Study FR01

The IAC will evaluate unblinded safety data from Study FR01 if

- 5 or more participants experience TEAEs in the same system organ class
- these TEAEs are serious (meeting at least 1 criterion which defines SAEs) or are assessed by the investigator as severe, or both, and
- these TEAEs are considered related to the blinded study intervention in the opinion of the investigator.

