4.6. Safety Analyses

For safety analyses, p-values will not be included unless specified in the ISA-SAP.

Table 4.1. Baseline and Postbaseline Period Definitions for Overall and Induction Safety Analyses

Analysis Type	Baseline Period	Postbaseline Period
TEAEs (induction safety analyses)	Starts from informed consent date for IMMB to just prior to the time of first dose.	Starts at the time of first dose of the study intervention and ends at the earliest of the following: 
 • Time of discontinuation from ISA • Time of discontinuation from study drug • Time of completing induction treatment period (time of the first dose in the maintenance treatment period, if relevant, or the date of the last visit in the induction treatment period), or • Database cut-off date for ongoing studies
TEAEs (overall safety analyses)	
Randomized in the initial period: Starts from informed consent date for IMMB to just prior to the time of first dose.
 
Assigned to Escape Arm from Placebo (if applicable): From the informed consent date for IMMB to just prior to the time of first dose of active study intervention on the escape arm.
	
For participants randomized to active study intervention in the initial period or assigned to escape arm from placebo: Starts at the time of first dose of the active study intervention and ends at the earliest of the following: 
 • Time of discontinuation from ISA • Time of ISA completion, or • Database cut-off date for ongoing studies 
 
For participants initially randomized to placebo: Starts at the time of first dose and ends at the earliest of the following: 
 • Time of discontinuation from ISA • Time of ISA completion • Time of first dose on the escape arm (if applicable), or • Database cut-off date for ongoing studies 

Analysis Type	Baseline Period	Postbaseline Period

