4.6.2. Adverse Events

Adverse events (AEs) are recorded in the electronic case report form (eCRF). Each AE will be coded to System Organ Classes (SOC) and Preferred Terms (PT), using the Medical Dictionary for Regulatory Activities (MedDRA) version that is current at the time of the database lock. Severity of AEs is recorded as mild, moderate, or severe.

TEAEs are defined as events that either first occurred or worsened in severity during the postbaseline period defined in [Table 4.1](#). The MedDRA Lowest Level Terms will be used in defining which events are treatment-emergent (TE). The maximum severity for each Lowest Level Term during the baseline period will be used as baseline. TE status in the presence of incomplete data will be determined through the following rules:

- if an AE has missing severity during the baseline period, then the baseline severity will be considered mild for determining TE status
- AEs with missing severity during the postbaseline period will be considered TE regardless of severity during the baseline period, and
- AEs with insufficient data on start date to determine the relevant period (for example, AE start year is the same as the treatment start year, but the AE start month and day are missing) will be considered TE.

For AEs occurring on the first day of the postbaseline period, the day and time of the AE start date will be compared with the dosing day and time. If such a comparison cannot be made due to incomplete day and time information, the AE will be considered TE.

Summaries of TEAE data will at a minimum include

- the number of participants in the safety population of interest
- the number of participants experiencing the event in the safety population of interest, and
- frequency, or percentage, relative to the safety population of interest.

As noted in [Table 4.2](#), some TEAE analyses will also include:

- person-years at-risk during the postbaseline period (years from start of postbaseline period to the first event of interest or the end of the postbaseline period, whichever is first), and
- (exposure-adjusted) IRs and corresponding confidence intervals.

For events that are sex specific, the denominator, computation of percentage, and IR will only include participants of the given sex.

System Organ Class mapping

MedDRA PTs are assigned to a SOC through primary mappings (defined by MedDRA). Thus, MedDRA PTs will appear in only 1 SOC.

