The planned summaries for AEs are provided in [Table 4.2](#)**Error! Reference source not found..**

Table 4.2. Tables and Listings Related to Adverse Events

Analysis	Details	Analyses
Overview of AEs	The number and percent of participants with: 
 • At least 1 TEAE • SAE • death, and • permanent discontinuation from study intervention due to an AE. 	Overall and Induction Analyses
TEAEs by PT within SOC	The number of participants, percent of participants, and IR of TEAEs using MedDRA PT nested within SOC. SOCs will be ordered by the difference in IRs between all LY and placebo.	Overall and Induction Analyses
Maximum Severity TEAEs by PT	
The number and percent of participants with TEAEs by maximum severity using MedDRA PT.
 
For each participant and TEAE, the maximum severity for the MedDRA PT is the maximum postbaseline severity observed from all associated LLTs mapping to the MedDRA PT.
 
The maximum severity will be determined based on the nonmissing severities. If all severities are missing for the defined postbaseline period of interest, it will show as missing in the table.
 
Events will be ordered by risk difference (total LY versus placebo) within SOC.
 
SOCS will be listed by risk difference.
	Induction Analysis
TEAEs occurring at $\geq 5\%$ by PT	The number of participants, percent of participants, and IR of TEAEs using MedDRA PT occurring in $\geq 5\%$ before rounding. Events will be ordered by decreasing difference in IRs.	Induction Analysis
Listing of AEs leading to permanent discontinuation of study intervention	Primary AE listed on the disposition form will be used and planned treatment group will be listed.	--
Listing of AEs leading to permanent discontinuation from study	Primary AE listed on the disposition form will be used and planned treatment group will be listed.	--
Listing of SAEs	SAEs resulting in death will be identified through a flag in the listing and planned treatment group will be listed.	--

Abbreviations: AE = adverse event; IR = incidence rate; LLT = Lowest Level Term; LY = Lilly product number; MedDRA = Medical Dictionary for Drug Regulatory Activities; PT = Preferred Term; SAE = serious adverse event; SOC = System Organ Class; TEAE = treatment-emergent adverse event.

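### Read literally, SAP Table 4.2 lets a Lowest Level Term that is not treatment-emergent set the severity grade of a TEAE under the same Preferred Term

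*SAP*

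**What the plan says.** The SAP supplied is the master-protocol SAP, which covers analyses common to all intervention-specific appendices (ISAs).

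**Emergence.** Section 4.6.2 states that "TEAEs are defined as events that either first occurred or worsened in severity during the postbaseline period". It makes that judgement at LLT level: "The maximum severity for each Lowest Level Term during the baseline period will be used as baseline". An LLT that continues after dosing at its baseline severity, or at a lower one, is therefore not treatment-emergent.

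**Grading.** The severity row of Table 4.2 reports "The number and percent of participants with TEAEs by maximum severity using MedDRA PT". For each participant and TEAE the grade is defined by this rule: "the maximum severity for the MedDRA PT is the maximum postbaseline severity observed from all associated LLTs mapping to the MedDRA PT".

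**Period.** The severity row is assigned to the induction analysis only. Under Table 4.1 that window closes when induction is completed, or sooner on other conditions, one of which is "Time of discontinuation from study drug". The Overview row and the row of TEAEs by PT within System Organ Class (SOC) cover both the overall and the induction periods, but neither carries severity.

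**The concern.** Emergence and severity are judged on different sets of LLTs. An LLT has to pass the emergence test to make the participant a case under a PT. The grade for that case is then taken from every LLT under the PT, and the only qualifier in the sentence is the mapping to the PT. A programmer who follows it as written would include LLTs that failed the emergence test.

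What is at stake is the accuracy of the severity columns. A participant can move from mild or moderate to severe because of an event that was already present, at that severity, before the first dose. The number of participants with a TEAE under the PT does not change.

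The period label raises a lesser question. The SAP names overall safety, across treatment periods and follow-up, as one of its two safety analyses. Its only severity table for all TEAEs stops at the end of induction.

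**Working it through.** The SAP gives no figure on this point, so there is none to reproduce. The check is a comparison of two rules, followed by one piece of arithmetic on the time window.

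**Inputs**
- Emergence per LLT, against that LLT's baseline maximum (SAP 4.6.2).
- Grade as the maximum over all LLTs under the PT, for participants with a TEAE (SAP Table 4.2).
- Induction of 16 weeks (Protocol 1.1); last dose at Week 40 (Protocol 1.3, Table 2); second follow-up visit about 12 weeks after the last dosing visit (Protocol 4.1).

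**Step 1: a worked case under one PT**

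| LLT | Baseline | Postbaseline | Emergent? |
|---|---|---|---|
| A | severe | severe | no |
| B | none | mild | yes |

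Maximum over all LLTs: severe. Maximum over emergent LLTs only: mild. If A were the only LLT, it would not be emergent and the participant would not be counted under this PT at all.

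**Step 2: how many patterns are affected**

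Code severity as none 0, mild 1, moderate 2, severe 3. An LLT with baseline b and postbaseline p is emergent if p > b.
- One LLT has 4 × 4 = 16 patterns: 6 emergent, 10 not. When the single LLT is emergent the two rules give the same grade.
- Two LLTs have 16 × 16 = 256 patterns. Neither is emergent in 10 × 10 = 100, so 256 − 100 = 156 have at least one emergent LLT.
- If both are emergent the rules agree. They differ only when one is emergent, the other is not, and the non-emergent one has the higher postbaseline severity:
  - emergent LLT mild (0→1: 1 pattern) with non-emergent LLT moderate (2→2, 3→2) or severe (3→3): 1 × 3 = 3
  - emergent LLT moderate (0→2, 1→2: 2 patterns) with non-emergent LLT severe (3→3): 2 × 1 = 2
  - emergent LLT severe: none
- Either LLT can be the emergent one, so (3 + 2) × 2 = **10 of 156** patterns change grade.
- The grade becomes severe in (1 + 2) × 2 = **6** of those 10. In all 6 the severe LLT is unchanged from baseline.

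The patterns are not equally likely, so 10/156 is not an expected rate.

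**Step 3: period covered by the severity row**

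Planned follow-up for a completer is 40 + 12 = 52 weeks. Induction covers 16. The remaining 52 − 16 = 36 weeks (36/52 = 69%) have no severity table for all TEAEs in this SAP. About 12 of those 36 weeks fall after the last dose.

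**The case against.** **The text can be read as limited to emergent LLTs.** The row is titled and populated by TEAEs, the grading sentence is framed per participant and per TEAE, and emergence has just been defined by LLT. That may well be the intention. But those words settle who is graded; the phrase naming which LLTs supply the grade has no such limit. The objection supports calling this a drafting fault, not leaving it as it is.

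**The situation needs a coincidence.** There must be two different LLTs under one PT, one persisting at the higher grade and not emergent, the other emergent and milder. This stands, and it is why the effect is probably small.

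**The induction-only label has a reason.** SAP Section 4.4 says that induction gives the cleanest comparison across ISAs, because every ISA has it and later periods differ. Other safety analyses are left to the ISA-SAP, which is not among the documents. This also stands, so the missing later severity table cannot be called an error.

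**Later events are not lost.** They appear in the overall TEAE table. SAEs, deaths and discontinuations due to AEs are counted in the overall Overview row. SAEs and AEs leading to discontinuation are listed, and narratives run to the end of participation (SAP 4.6.3). What remains is narrow: later severe TEAEs that are neither serious nor lead to discontinuation carry no grade in a summary table.

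**Conclusion.** The point holds as a wording fault with a limited effect. Followed literally, the rule can give a TEAE the grade of a non-emergent LLT under the same PT. It never does so with a single LLT, and it never adds a TEAE. The documents do not allow a frequency to be estimated. The period point is secondary and optional, and depends on what the ISA-SAP contains.

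A reader might infer more, but the documents do not support it:
- *That severe-TEAE rates are inflated by some stated amount, diluting the active-to-placebo ratio.* No rate of persisting severe baseline events or of sibling LLTs is given. The SAP's safety estimands are differences in incidence rates, and the severity row is ordered by risk difference. An equal addition to both arms would leave a risk difference unchanged.
- *That flares during washout of atopic dermatitis treatment make this common in FR01.* The documents do not say that such flares are recorded as AEs; the instructions for AE collection are in the master protocol, which was not supplied.
- *That the stopping rule is weakened.* The committee review in Protocol Attachment 3 is triggered by accumulating related serious or severe TEAEs, and does not depend on Table 4.2.
- *That all later severe events are omitted.* This is true of the one row only.

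**What to change.** In the severity row of Table 4.2, insert the word treatment-emergent before LLTs, so that the maximum is taken over the treatment-emergent LLTs mapping to the PT. Apply the same limit to the row's next rule, on missing severities, so that an emergent event with no recorded severity shows as missing and does not borrow a grade from a non-emergent LLT. The cost is a wording edit and a matching line in the programming specification; no new data are needed.

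Optionally, and only if the ISA-SAP does not already cover it, either add a line for participants with at least one severe TEAE to the Overview row, or assign the severity row to both the overall and the induction analyses. The downside is one more output.

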2.1. Multiplicity Adjustment

Multiplicity adjustment will generally not be performed for ISAs; refer to Section 2.1 of the ISA-SAP for specific details.

3. Analysis Sets

The populations in [Table 3.1](#) are defined for this study. Depending on the ISA, the modified intent to treat (mITT) and/or safety population may distinguish between induction and maintenance periods. For example, a safety population for the induction period and, separately, a safety population for the maintenance period.

Table 3.1. The Minimum Analysis Sets for the ADMP

Participant Analysis Set	Description
mITT	All randomized participants receiving at least 1 dose of study intervention. Participants will be included in the analysis set according to their randomly assigned intervention.
Safety	All randomized participants receiving at least 1 dose of study interventions. Participants will be included in the analysis set according to the intervention they actually received.

Abbreviations: ADMP = atopic dermatitis master protocol; mITT = modified intent to treat.

4. Statistical Analyses

The MP-SAP will specify analyses and methods for

- patient disposition information
- baseline demographic and disease severity information

CCI

- safety analyses applicable across all ISAs.

The ISA-SAP will specify efficacy estimands and corresponding methodology, and other safety analyses.

[figure not shown]

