4.4. Secondary Endpoints/Estimands Analysis

The MP-SAP will focus on two safety analyses: (1) overall safety profile across treatment periods including posttreatment follow-up, and (2) safety profile during induction. The ISA-SAP will define the treatment groups, if relevant, for the overall and induction safety analyses.

Please see Section 4.4 of the relevant ISA-SAP for secondary endpoints and/or estimands for efficacy analyses or ISA-specific safety analyses.

Estimand for overall safety analyses

A secondary clinical question of interest is: what is the difference between active study intervention versus placebo in the number, percent, and/or incidence rates (IRs) of treatment-emergent adverse events (TEAEs) of interest?

The estimand is described by the following attributes:

- Population: participants with moderate-to-severe AD
- Endpoint(s): number, percent, and/or IRs for first TEAEs of interest
- How to account for intercurrent events:
 - Early Permanent Discontinuation of Study Intervention: TEAEs during the posttreatment follow-up will be considered attributable to the study intervention
 - Use of Prohibited or Rescue Medication: TEAEs after the use of prohibited or rescue medication will be considered attributable to the study intervention.

- Assignment to Escape Arm (if applicable): if a participant escapes from placebo to active study intervention, subsequent TEAEs will be attributable to the active study intervention, and
- Assignment to Placebo Withdrawal Arm (if applicable): if a participant is re-randomized from active study intervention to placebo, TEAEs will be considered attributable to the active study intervention until the completion of the study
- Population-level summary: the difference in IRs for TEAEs of interest between participants receiving (rather than assigned to) active study intervention versus placebo, and
- Rationale for estimand:
 - TEAEs of interest for participants receiving active study intervention are considered attributable to study intervention

CCI

- the use of prohibited or rescue medication are potential components of treatment regimens and should therefore be attributable to study intervention.

Secondary estimand for safety during induction period

A secondary clinical question of interest is: what is the difference between the active study intervention versus placebo (or active comparator) in the number, percent, and/or IRs of TEAEs of interest during the induction treatment period?

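### Do the SAE and AE-discontinuation listings, labelled by planned treatment group, misattribute events that occur on escape therapy?

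*SAP*

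**What the plan says.** Table 4.2 in SAP Section 4.6.2 plans three participant-level AE listings. For SAEs, "SAEs resulting in death will be identified through a flag in the listing and planned treatment group will be listed". For AEs leading to discontinuation of study intervention, and again for those leading to discontinuation from the study, "Primary AE listed on the disposition form will be used and planned treatment group will be listed". The table does not define the planned group. Its Analyses column shows a dash for all three listings, whereas the summary tables are marked Overall, Induction or both.

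Elsewhere the SAP works by treatment received. For the Safety set in Section 3, Table 3.1: "Participants will be included in the analysis set according to the intervention they actually received". The overall safety estimand in Section 4.4 compares "the difference in IRs for TEAEs of interest between participants receiving (rather than assigned to) active study intervention versus placebo". It has a rule for escape, "if a participant escapes from placebo to active study intervention, subsequent TEAEs will be attributable to the active study intervention", and one for re-randomisation from active drug to placebo, where "TEAEs will be considered attributable to the active study intervention until the completion of the study". Table 4.1 puts the escape rule into effect. It closes the placebo period at the first escape dose and gives these participants a new baseline: "From the informed consent date for IMMB to just prior to the time of first dose of active study intervention on the escape arm".

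Protocol Sections 4.1 and 6.4 confirm that FR01 has such an escape arm, open from Week 16. Week 16 responders on one active regimen are re-randomised between active drug and placebo.

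**The concern.** The summary tables follow the drug received, while the case listings carry a planned label. Suppose a placebo participant moves to active escape at Week 16 and has an SAE at Week 30. The overall tables count that event under LY3454738. If planned means the Week 0 arm, the listing shows it under placebo.

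This could matter because Table 4.2 plans no SAE table by preferred term. SAEs appear there only as a count in the AE overview, so within that table the listing is where a reader sees which SAE occurred in whom. In a Phase 2 study of about 260 participants, such events are read case by case. A placebo label on an active-drug event could obscure a pattern and would not reconcile with the overview count. The labels also vary: the serious-infection and opportunistic-infection listings in Table 4.6 and the abnormal-laboratory listing in Table 4.3 refer only to treatment group. One serious infection could therefore appear in two listings with different labels.

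**Working it through.** The plan states no figure to reproduce here. The check is to follow each participant path through the overall attribution rule (Section 4.4 with Table 4.1) and through the possible meanings of the listing label.

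| Participant path and event | Overall tables | Label = Week 0 arm | Label = treatment planned for the period | Label = treatment at onset |
|---|---|---|---|---|
| Any arm, event before Week 16, dosed as assigned | as assigned | same | same | same |
| Placebo throughout | placebo | placebo | placebo | placebo |
| Placebo, then active escape; event on escape | LY | **placebo** | LY | LY |
| LY, then re-randomised to placebo; event on placebo | LY | LY | **placebo** | **placebo** |
| LY throughout, or LY then escape | LY | LY | LY | LY |

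Three points follow.

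1. Each reading of the planned group departs from the attribution rule on one path only: the Week 0 reading on placebo-to-escape, the period reading on placebo withdrawal.
2. Treatment at onset departs on the withdrawal path too. A single onset label would move the disagreement between listing and tables, not remove it.
3. Nothing departs during induction, because escape and re-randomisation start at Week 16.

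**What depends on the label.** SAEs, deaths and AE-related discontinuations of study intervention are counted in the AE overview, which is assigned to both the overall and induction analyses and uses the Table 4.1 periods. No count, percentage or incidence rate is taken from a listing.

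**How often it could arise.** The placebo arm is 68 (Protocol Section 4.1). The escape threshold is redacted, so the placebo response rate r at that threshold is an assumption. Number escaping at Week 16 = 68 × (1 − r):

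- r = 12% (the placebo EASI-75 rate in Protocol Section 9.5, relevant only if the threshold is EASI-75): 68 × 0.88 = 59.8
- r = 30%: 68 × 0.70 = 47.6
- r = 50%: 68 × 0.50 = 34.0
- r = 60%: 68 × 0.40 = 27.2

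The path is therefore common, roughly 40% to 88% of the placebo arm. To turn this into listing rows, assume full follow-up from Week 16 to Week 52 and an SAE rate per person-year that the documents do not give. Expected SAEs after escape = rate × 68 × (1 − r) × 36/52:

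- rate 0.02: 0.47 (r = 50%) to 0.83 (r = 12%)
- rate 0.05: 1.18 to 2.07
- rate 0.10: 2.35 to 4.14

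For a given rate and r, these run high for the Week 16 escapers. They allow no dropout, and Protocol Section 7.1.2 stops study drug in escape non-responders, who may leave before Week 52. Escapes after Week 16 are not included.

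**Other planned displays of the same events.** SAP Section 4.6.3 requires narratives with patient-level data for deaths, SAEs and permanent discontinuations of study intervention due to AEs. Serious infections have their own listing with start date and relationship to treatment (Table 4.6). An internal committee reviews unblinded safety data (Protocol Section 4.1), and related TEAEs that are serious or severe can trigger its review (Protocol Attachment 3).

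**The case for a change.** The strongest case for a change is that the mismatch is visible in the text, affects a large part of the placebo arm and would cost little to remove. Nothing in Table 4.2 asks for treatment at onset, escape status or attribution group, and neither reading of the label agrees with Section 4.4 on every path. A reader with only the SAE listing and the overview table could fail to reconcile them.

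The ambiguity stands, and so does the inconsistent labelling across Tables 4.2, 4.3 and 4.6. Two further claims do not. The first is that the listings break the SAP's attribution rule. That rule belongs to an estimand expressed as numbers, percentages and incidence rates; the overall tables apply it, and the listings are marked as part of neither analysis. The second is that a signal would be hidden. The overview counts place post-escape events under active drug, and each SAE has a narrative. A share of placebo follow-up spent on escape does not measure the problem either, since a listing has no denominator.

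It also cannot be shown that events would be listed under placebo at all. Escape is itself a protocol-planned regimen, and Section 4.4 leaves treatment groups for the overall and induction analyses to the ISA-SAP, which is not among the documents.

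**Conclusion.** No change to the plan follows. The platform-level SAP leaves a listing label undefined, a detail normally settled when the study's output shells are drawn up. Naming the planned group does not stop a programmer from also showing the treatment sequence or the treatment at onset. Whichever meaning is used, no safety count, percentage, incidence rate or conclusion moves.

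The effect is limited to the label on perhaps 0.5 to 4 SAE rows, plus any matching discontinuation rows, under the Week 0 reading. That range rests on an assumed SAE rate of 0.02 to 0.10 per person-year, an assumed 50% to 88% of placebo participants escaping at Week 16, and complete follow-up to Week 52. The conclusion itself does not depend on those assumptions. It rests on the listings lying outside both safety analyses, on Table 4.1 carrying the attribution rule into the overall tables, and on narratives covering SAEs and AE-related discontinuations of study intervention.
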